6. In an ideal scenario, at which time points during surgery would you like to be updated? (Check all that apply)

Patient is entering the OR  
 Initial skin incision has been made  
 Critical part of the case is complete, and closure is about to begin  
 Closure is complete, and patient will be transferred to the recovery room when ready  
 Patient is leaving the OR

7. Please check all that apply regarding the amount of detail in the updates you received during the perioperative period.

- Updates were too detailed
- Updates were lacking enough detail
- I was satisfied with the amount of detail in the updates

8. In your opinion, what would be the ideal method to deliver updates to family members during surgery?

- Human communication
- Text message
- Pager
- Application for electronic device (cell phone, tablet, etc.)
- Television Screen in the Waiting Room

9. At what point during the perioperative period would you prefer to have a consult with the surgeon? Please select one answer.

- Critical part of the case is complete, and closure is about to begin
- Closure is complete
- Upon transfer to the recovery room

10. Were you aware the University of Vermont Medical Center has a new website that allows family members to track the status of their loved one in the OR?

- Yes

*If yes, did you utilize this website (circle one): Yes / No*

- No

11. Please feel free to provide any feedback and/or suggestions regarding the communication with family members during the perioperative period.

---

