**For Research Team to complete:**

Date of Procedure:

Time into OR:

Time out of OR:

Length of the procedure:

Type of Procedure:

Surgeon:

Spinal vs. GA:

Group:

Thank you for taking the time to take part in our survey! The data from this study will allow us to identify family preferences regarding updates from the surgical team. This information can then be used to improve patient and family satisfaction in the perioperative period.

*Family Member Demographic Information*

Age: \_\_\_\_\_

Sex (circle one): F / M / Other

Highest educational degree you have attained (check one):  High School diploma or equivalent (GED)  
 Associate degree  
 Vocational degree  
 Bachelor's degree  
 Master's degree  
 Professional degree  
 None of the above

1. How are you related to the patient (i.e parent, spouse, partner, son, daughter, etc)?

2. Please rate your level of satisfaction with your overall experience today in the perioperative area by circling the answer that best describes your satisfaction (with 1 being extremely unsatisfied and 5 being extremely satisfied).

|             |               |              |                 |               |                |
|-------------|---------------|--------------|-----------------|---------------|----------------|
| None at all | Extremely low | Somewhat low | Not high or low | Somewhat high | Extremely high |
| 0           | 1             | 2            | 3               | 4             | 5              |

3. Please rate your level of anxiety during the surgery by circling the answer that best describes your anxiety (with 0 being none at all and 5 being extremely high).

|             |               |              |                 |               |                |
|-------------|---------------|--------------|-----------------|---------------|----------------|
| None at all | Extremely low | Somewhat low | Not high or low | Somewhat high | Extremely high |
| 0           | 1             | 2            | 3               | 4             | 5              |

4. Please rate your level of satisfaction with the number of updates provided during the perioperative period (with 1 being extremely unsatisfied and 5 being extremely satisfied).

|             |               |              |                 |               |                |
|-------------|---------------|--------------|-----------------|---------------|----------------|

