## PURPOSE AND OBJECTIVES

**Purpose:** The importance of the research and the potential knowledge to be gained should be explained in detail. Give background information.

Multiple studies have shown that perioperative communication is important in reducing family member anxiety and improving the overall experience of family members waiting for surgical patients. In fact, perioperative communication and attentiveness have been identified as the two most important determinants of perceived surgeon performance. Moreover, surgeons agree that perioperative communication is important and report feeling as though the patients' family members are pseudo-patients, requiring attention and treatment, and perceive reduced family anxiety as a necessary component toward understanding post-operative status updates and findings.

Communication and empathy is even more important in the case of adverse outcomes. Family members of ICU patients rated attitude, clarity of message, and ability to ask questions as most important when receiving bad news. The CARE/SHARE models of establishing rapport with patients and families suggests it is best to wait until all information is available before speaking with the family, particularly in the event of adverse surgical outcomes. However, presently there is no agreed upon standardized time to deliver post-operative news to patients' families, with some surgeons delivering news before a procedure is entirely complete.

We have identified several times at which different surgeons deliver news in the perioperative period: 1) As soon as the major part of the procedure is completed, 2) While the patient is sutured at the close of the surgery, 3) Once the patient is extubated, and 4) Once all auxiliary information is obtained (x-rays, neurovascular examination, etc.) and the patient is awake. While there is anecdotal evidence that it may be concerning to patients' families to not receive an update at the scheduled ending time of a procedure, actual family preference remains undetermined. In a study by Blum et al, families were surveyed regarding perioperative stress and experience satisfaction. Those receiving periodic updates from a circulating nurse (calling every two hours) reported less anxiety and a better overall experience than the group of families who did not receive periodic updates. However, no study currently exists that examines the optimal timing and level of detail of surgeon-family communication.

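### Survey item 9 forces a choice among three surgeon-consult times and omits one the protocol itself lists, so the reported preference holds only for the options offered

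*Combined protocol and SAP*

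**What the plan says.** Item 9 of the attached family survey reads "At what point during the perioperative period would you prefer to have a consult with the surgeon? Please select one answer". Its three answers are the end of the critical part with closure about to start, the end of closure, and the move to the recovery room. It has no residual answer. Both copies of the form carry the same list.

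The protocol's Purpose and Objectives section approaches the same question from the surgeons' side: "We have identified several times at which different surgeons deliver news in the perioperative period". It names four times. The first two are completion of the major part and the suturing at the end. The third is "3) Once the patient is extubated" and the fourth is "4) Once all auxiliary information is obtained (x-rays, neurovascular examination, etc.) and the patient is awake". The same section calls families' actual preference undetermined. It cites rapport models whose advice "suggests it is best to wait until all information is available before speaking with the family", and adds that this applies especially after adverse surgical outcomes.

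The closing text of the survey tells respondents that the data will be used to "identify family preferences regarding updates from the surgical team". The stated objective, however, is the effect of strategic communication on satisfaction, anxiety and overall experience; preference is not listed there. Statistical Considerations specifies no analysis of item 9. Item 11 is an open comment field on communication with families.

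**The concern.** Item 9 is the only closed question on when families want the surgeon to speak to them. It asks about the whole perioperative period, so the fourth time falls within the question but not within the answers. A family that would rather wait for full information must tick a time it does not prefer, skip the item, or volunteer the point in item 11. None of these puts it in the item 9 tally.

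At stake is the descriptive preference result. The protocol presents timing as an evidence gap and tells families that their preferences will be identified. As written, item 9 cannot show whether families prefer to wait until everything is known, which is one of the practices the protocol describes. A larger sample does not cure this, and because the form carries no identifying information, most families could not be asked again.

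**Working it through.** **1. Options set side by side.**

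| Time listed in Purpose and Objectives | Counterpart in item 9 |
|---|---|
| Major part completed | First option (critical part done) |
| During suturing | Roughly the first or second option (around closure) |
| Extubation | Not named; the third option (transfer to recovery) may roughly stand in |
| All auxiliary information in, patient awake | None |

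Only one of the four times clearly has no counterpart. The form does use a residual answer elsewhere: the education question has a none-of-these box.

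**2. Is there a figure to reproduce?** The plan gives none for the preference items. Its one computed figure, 96 participants, concerns anxiety ratings. It cannot be rebuilt because the means and standard deviations are not stated. Here 96 (Statistical Considerations) and the anticipated 200 (Number of Subjects) serve only as denominators, assuming every family answers item 9.

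**3. Proportional spread (assumption).** Let q be the true share preferring the omitted time. The documents do not give q, so 10% to 30% is purely illustrative. If these families spread over the listed options in proportion, or leave the item blank and are dropped from the denominator, then

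reported share r = true share / (1 − q), so overstatement = r − r(1 − q) = r × q.

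For a reported share of 30%:
- q = 10%: 0.30 × 0.10 = 3 points
- q = 30%: 0.30 × 0.30 = 9 points
- q = 0: no error

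Sampling error for the same share is 1.96 × √(0.30 × 0.70 / n):
- n = 96: 9.2 points
- n = 200: 6.4 points

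Under this pattern the distortion stays within the sampling half-width at n = 96. At n = 200 it passes the half-width once q exceeds 6.4 / 30 = 21%.

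**4. Concentration on one option (assumption).** Suppose the remaining families split 20/30/50 over the three options, and all of q moves to the latest one, which lies nearest to the omitted time. Its true share is 0.5(1 − q) and its reported share is 0.5(1 − q) + q.

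| q | True share | Reported share | Error |
|---|---|---|---|
| 10% | 45% | 55% | 10 points |
| 20% | 40% | 60% | 20 points |
| 30% | 35% | 65% | 30 points |

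The half-width near 50% is 1.96 × √(0.25 / n), about 10 points at n = 96 and 7 at n = 200. Under this pattern the error equals or exceeds sampling error.

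**5. When would the omitted time be the true favourite?** With the 20/30/50 split, when q > 0.5(1 − q), that is q above 33%. With an equal split, when q > (1 − q)/3, that is q above 25%.

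**The case against.** The strongest reply is that this touches nothing the trial is powered for. Preference is not in the stated objective or among the outcomes in Statistical Considerations. The surgeon's talk follows usual practice in both groups, so item 9 does not concern the tested intervention. Items 2 to 4, which carry the satisfaction and anxiety ratings, are untouched. All of this stands and limits the point to the preference result.

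Item 11 lets a family state another preference. That is a partial remedy: the field is general and unprompted, and it does not correct the item 9 counts.

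The cited models favour waiting mainly after adverse outcomes, so they do not show that families in general prefer it. That also stands. The point rests on the protocol listing the time as current practice, not on the models.

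A reader might infer that item 6 has the same defect. It asks "In an ideal scenario, at which time points during surgery would you like to be updated" and offers only surgical events, whereas the cited study used fixed intervals: "Those receiving periodic updates from a circulating nurse (calling every two hours) reported less anxiety". The documents do not support this. Those calls were a nurse-delivered intervention in another study, not one of the listed surgeon times. Item 6 allows any number of ticks, so nobody is forced into one answer, and the arithmetic above does not transfer to it.

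**Conclusion.** The point holds for item 9 alone. The item omits a surgeon-consult time that the protocol lists, demands a single answer and has no residual box. What is certain is that its result is conditional on three options. Whether it is distorted, and by how much, depends on a share the documents do not give. The illustrative 3 to 9 points (proportional spread, reported share 30%) and 10 to 30 points (all on the latest option) rest on the assumed q of 10% to 30%.

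Two stronger readings fail. A reader might infer that the reported preference will be wrong; with q unknown, the error could be nil. A reader might also infer that the survey cannot contradict the study's hypothesis. It can: the hypothesis concerns satisfaction from strategic updates, which the randomised comparison on items 2 to 4 tests directly. Families can also say in item 5 that updates were too frequent.

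This is an inexpensive improvement to a descriptive result, with no effect on the group comparison or the sample size.

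**What to change.** In both copies of the form, add three answers to item 9:
- *once all information (such as x-rays and examination) is available and the patient is awake*
- *other: ____*
- *no preference*

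A separate extubation answer is not needed. The form records spinal versus general anaesthesia, and extubation may not apply to spinal cases. Item 6 can stay as it is.

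If forms have already been collected, report item 9 separately for the old and new forms, and describe the old-form results as conditional on the three options offered.

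The cost is three tick boxes on a survey that the amendment is already changing. The one real downside is that old-form and new-form answers to item 9 cannot be pooled.

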**For Research Team to complete:**

Date of Procedure:

Time into OR:

Time out of OR:

Length of the procedure:

Type of Procedure:

Surgeon:

Spinal vs. GA:

Group:

Thank you for taking the time to take part in our survey! The data from this study will allow us to identify family preferences regarding updates from the surgical team. This information can then be used to improve patient and family satisfaction in the perioperative period.

*Family Member Demographic Information*

Age: \_\_\_\_\_

Sex (circle one): F / M / Other

Highest educational degree you have attained (check one):  High School diploma or equivalent (GED)  
 Associate degree  
 Vocational degree  
 Bachelor's degree  
 Master's degree  
 Professional degree  
 None of the above

1. How are you related to the patient (i.e parent, spouse, partner, son, daughter, etc)?

2. Please rate your level of satisfaction with your overall experience today in the perioperative area by circling the answer that best describes your satisfaction (with 1 being extremely unsatisfied and 5 being extremely satisfied).

|             |               |              |                 |               |                |
|-------------|---------------|--------------|-----------------|---------------|----------------|
| None at all | Extremely low | Somewhat low | Not high or low | Somewhat high | Extremely high |
| 0           | 1             | 2            | 3               | 4             | 5              |

3. Please rate your level of anxiety during the surgery by circling the answer that best describes your anxiety (with 0 being none at all and 5 being extremely high).

|             |               |              |                 |               |                |
|-------------|---------------|--------------|-----------------|---------------|----------------|
| None at all | Extremely low | Somewhat low | Not high or low | Somewhat high | Extremely high |
| 0           | 1             | 2            | 3               | 4             | 5              |

4. Please rate your level of satisfaction with the number of updates provided during the perioperative period (with 1 being extremely unsatisfied and 5 being extremely satisfied).

|             |               |              |                 |               |                |
|-------------|---------------|--------------|-----------------|---------------|----------------|
| None at all | Extremely low | Somewhat low | Not high or low | Somewhat high | Extremely high |
| 0           | 1             | 2            | 3               | 4             | 5              |

5. Please check all that apply regarding the frequency of updates you received during the perioperative period.

Updates were too frequent  
 Updates were too infrequent  
 I was satisfied with the number of updates I received

6. In an ideal scenario, at which time points during surgery would you like to be updated? (Check all that apply)

Patient is entering the OR  
 Initial skin incision has been made  
 Critical part of the case is complete, and closure is about to begin  
 Closure is complete, and patient will be transferred to the recovery room when ready  
 Patient is leaving the OR

7. Please check all that apply regarding the amount of detail in the updates you received during the perioperative period.

- Updates were too detailed
- Updates were lacking enough detail
- I was satisfied with the amount of detail in the updates

8. In your opinion, what would be the ideal method to deliver updates to family members during surgery?

- Human communication
- Text message
- Pager
- Application for electronic device (cell phone, tablet, etc.)
- Television Screen in the Waiting Room

9. At what point during the perioperative period would you prefer to have a consult with the surgeon? Please select one answer.

- Critical part of the case is complete, and closure is about to begin
- Closure is complete
- Upon transfer to the recovery room

10. Were you aware the University of Vermont Medical Center has a new website that allows family members to track the status of their loved one in the OR?

- Yes  
*If yes, did you utilize this website (circle one): Yes / No*
- No

11. Please feel free to provide any feedback and/or suggestions regarding the communication with family members during the perioperative period.

---

**For Research Team to complete:**

Date of Procedure:

Time into OR:

Time out of OR:

Length of the procedure:

Type of Procedure:

Surgeon:

Spinal vs. GA:

Group:

## Human Subjects Research Protocol

The Common Human Subjects Protocol Cover Form **must** be completed and **attached** to the front of this form. This Protocol form should be completed for any human subjects research proposal that does not have a specific "protocol," such as a grant application. This form must be submitted along with a copy of the complete grant proposal and all the information in this form **must** be consistent with that proposal. This protocol form, once IRB approved, will be the working protocol for that research. **When completing this document, do not refer to page numbers within your grant.** If revisions are necessary during the course of the research, amendments should refer to this protocol form, not the grant proposal. Enter responses for all sections. Check N/A if the section does not apply.

### PROTOCOL SUMMARY

Project Title:

Protocol Version Date:

Perioperative Surgeon-Family Communication

4/14/16

Principal Investigator: [name]

Grant Sponsor: N/A

Grant Number: N/A

(For grants routed through UVM, indicate the OSP Proposal ID # located at the top of the OSP Routing Form)

**Lay Language Summary:** (Please use non-technical language that would be understood by nonscientific IRB members to summarize the proposed research project. The information must include: (1) a brief statement of the problem and related theory supporting the intent of the study, and (2) a brief but specific description of the procedure(s) involving the human subjects. Please do not exceed one single-spaced 8 1/2 X 11" page.)

It has been shown that perioperative communication plays an important role in reducing family member anxiety and improving overall satisfaction while they are waiting for surgical patients. As the notion of patient and family centered care has evolved over the years, it has become clear that patients' family members require attention and care during the perioperative period. Studies have suggested that family members who received periodic updates during their loved ones' surgeries report less anxiety and a better overall experience than families who do not receive the periodic updates. However, there have been no studies conducted that investigate the optimal timing and level of detail of the surgeon-family communication. The proposed study aims to determine the effect of strategic communication with patients' relatives during the perioperative period on their satisfaction, anxiety and overall experience. We hypothesize that the greatest patient and family satisfaction would come from receiving critical strategic updates during vital time points of the surgical procedure.

This will be a survey-based study. On the day of the surgery, a research team member will inform the patient and family that a study is being conducted to investigate the effect of perioperative communications on family satisfaction and anxiety. It will be explained that each family will randomly be assigned to two communication pathways, and there will be a short survey for them to complete post-surgery. In the control pathway, the surgeon will communicate with the family per his/her usual practice near the completion of the surgical procedure. In the intervention group, the families will receive additional standardized electronic updates via pagers at three pivotal moments: 1) Initial skin incision has been made, 2) Critical part of the case is completed and closure has begun, 3) Closure is complete, and patient is about to be transferred to the recovery room. Then, the surgeon will communicate the final update near the end of the surgical procedure per his/her usual practice.

After the surgery is complete, and both control and intervention groups have received the final update, a research team member will locate the waiting family and administer the post-operative survey rating their satisfaction and anxiety levels using Likert scale questions (1-5 scale). In addition to the survey, basic demographic information of the patient and family member completing the survey, as well

as the number of people in the waiting party, will be reported.

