**Family Member Demographic Information**

Age: \_\_\_\_\_

Sex (circle one): F / M / Other

Highest educational degree you have attained (check one):  High School diploma or equivalent (GED)  
 Associate degree  
 Vocational degree  
 Bachelor's degree  
 Master's degree  
 Professional degree  
 None of the above

1. How are you related to the patient (i.e parent, spouse, partner, son, daughter, etc)?

2. Please rate your level of satisfaction with your overall experience today in the perioperative area by circling the answer that best describes your satisfaction (with 1 being extremely unsatisfied and 5 being extremely satisfied).

|             |               |              |                 |               |                |
|-------------|---------------|--------------|-----------------|---------------|----------------|
| None at all | Extremely low | Somewhat low | Not high or low | Somewhat high | Extremely high |
| 0           | 1             | 2            | 3               | 4             | 5              |

3. Please rate your level of anxiety during the surgery by circling the answer that best describes your anxiety (with 0 being none at all and 5 being extremely high).

|             |               |              |                 |               |                |
|-------------|---------------|--------------|-----------------|---------------|----------------|
| None at all | Extremely low | Somewhat low | Not high or low | Somewhat high | Extremely high |
| 0           | 1             | 2            | 3               | 4             | 5              |

4. Please rate your level of satisfaction with the number of updates provided during the perioperative period (with 1 being extremely unsatisfied and 5 being extremely satisfied).

|             |               |              |                 |               |                |
|-------------|---------------|--------------|-----------------|---------------|----------------|
| None at all | Extremely low | Somewhat low | Not high or low | Somewhat high | Extremely high |
| 0           | 1             | 2            | 3               | 4             | 5              |

5. Please check all that apply regarding the frequency of updates you received during the perioperative period.

Updates were too frequent  
 Updates were too infrequent  
 I was satisfied with the number of updates I received

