Prior to the surgery, a member of the research team will review each case to determine if the surgery meets study criteria. The exclusion criteria include: surgeries lasting less than two hours, patients under the age of 18, non-speaking patients and/or families, or patients that do not have family members present in the pre-operation area. On the day of the surgery, a research team member will inform the patient and family that a study is being conducted to investigate the effect of perioperative communications on family satisfaction and anxiety. It will be explained that each family will randomly be assigned to two communication pathways, and there will be a short survey for them to complete post-surgery. In the control pathway, the surgeon will communicate with the family per his/her usual practice near the completion of the surgical procedure. In the intervention group, the families will receive additional standardized electronic updates via pagers at three pivotal moments: 1) Initial skin incision has been made, 2) Critical part of the case is completed and closure has begun, 3) Closure is complete, and patient is about to be transferred to the recovery room. A member of the surgical team will be responsible for sending these updates. Then, the surgeon will communicate the final update near the end of the surgical procedure per his/her usual practice.

After the surgery is complete, and both control and intervention groups have received the final update, a research team member will locate the waiting family and administer the post-operative survey rating their satisfaction and anxiety levels using Likert scale questions (1-5 scale). We adopted a previously used survey and modified it accordingly. In addition to the survey, basic demographic information of the patient and family member completing the survey, as well as the number of people in the waiting party, will be reported. When the family member has completed the survey, they will leave the survey in a secure drop box in the waiting area.

To ensure that the results of the survey are reproducible, we will take twenty subjects who completed the survey and ask permission to call them one day after the initial survey. We will then compare the results of the two surveys.

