**Not applicable**

**Recruitment:** Describe plans for identifying and recruitment of subjects. All recruitment materials (flyers, ads, letters, etc) need to be IRB approved prior to use.

PI/Collaborators will recruit their own patient's and their families

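### Pages are sent from within the surgical team in intervention cases only, so the surgeon can learn the arm before an unscripted final talk that precedes the survey in both arms

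*Combined protocol and SAP*

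**What the plan says.** The Procedures text (Methods and Procedures) and the Lay Language Summary (Protocol Summary) describe the two arms alike. For controls: "In the control pathway, the surgeon will communicate with the family per his/her usual practice near the completion of the surgical procedure". In the intervention arm, "the families will receive additional standardized electronic updates via pagers at three pivotal moments": skin incision, start of closure, and end of closure. Procedures adds who sends them: "A member of the surgical team will be responsible for sending these updates". After the pages comes the surgeon's talk: "Then, the surgeon will communicate the final update near the end of the surgical procedure per his/her usual practice".

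The survey is handed out only afterwards: "After the surgery is complete, and both control and intervention groups have received the final update". Item 2 asks: "Please rate your level of satisfaction with your overall experience today in the perioperative area". Item 4 rates the number of updates over the whole perioperative period, and items 5 and 7 ask whether updates were too many, too few, too detailed or not detailed enough. Item 3 asks about anxiety during the surgery.

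On the surgeons' role, the Recruitment section says: "PI/Collaborators will recruit their own patient's and their families". The Inclusion/Exclusion Criteria limit entry to families of patients of the surgeons taking part in the study.

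**The concern.** The surgeon's talk is meant to be common to both arms, so that the arms differ only by the pages. That holds only if the talk does not depend on the arm. Here the operating room behaves differently by arm from skin incision onward, because a team member sends pages in one arm and not in the other. A surgeon who notices could come out sooner or say more to a family that has heard nothing, or take more care with a family in the paged arm. Either could happen without intent.

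An arm-dependent talk would be credited to the pages or subtracted from them. This is separate from concealing the allocation at enrolment: the exposure arises after assignment and would remain if assignment were perfectly concealed. Enrolling more families would not remove it.

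**Working it through.** **1. Can the surgeon learn the arm before the talk?**

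| Step | Control | Intervention | Source |
|---|---|---|---|
| Incision, closure start, closure end | no page | page sent by a surgical-team member | Procedures |
| Surgeon's talk | usual practice | usual practice, after the pages | Lay Language Summary; Procedures |
| Survey | after the talk | after the talk | Lay Language Summary; Procedures |

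The sender's role is not specified beyond team membership. No section masks the surgeon, places the sender outside the team, scripts the talk, or records its time, length or content. The research-team form at the end of the survey records surgeon, group, and times into and out of the operating room, but not the time of the talk.

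**2. Is there room for the talk to vary?** Yes. The Purpose section says there is no agreed time for giving families the news and lists four times that different surgeons use. Usual practice is the only constraint.

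**3. Which outcomes can the talk reach?**

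- Items 2 and 4 (overall experience; number of updates): directly, since the talk is part of the experience and is itself an update.
- Items 5 and 7 (frequency and detail): directly, for the same reason.
- Item 3 (anxiety during surgery): mainly through recall, or directly if the surgeon speaks before the operation ends.

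**4. The plan's own figure.** Statistical Considerations gives 96 in total, 48 per arm, for power 0.8 at significance 0.05, based on anxiety ratings from a cited study. The means and SDs are not given, so 96 cannot be reproduced forward. Neither the test nor its sidedness is stated. Back-solving for a standardised difference d:

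- two-sided: d = (1.960 + 0.842) × √(2/48) = 2.802 × 0.2041 = 0.572 (0.578 with a t-test);
- one-sided: d = (1.645 + 0.842) × 0.2041 = 0.508 (0.511 with a t-test).

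**5. A generic illustration of size.** Assume a net arm-dependent shift b, in SD units, no true page effect, and a two-sided 5% test with normal approximation. The documents give no value for b. With SE = √(2/n), where n is the number per arm:

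P(reject) = 1 − Φ(1.960 − b/SE) + Φ(−1.960 − b/SE).

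For b = 0.2 and n = 48: b/SE = 0.2/0.2041 = 0.980, so P = 1 − Φ(0.980) + Φ(−2.940) = 0.165. The second column of results uses 100 per arm, half of the roughly 200 subjects anticipated under Number of Subjects.

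| b (SD) | 48 per arm | 100 per arm |
|---|---|---|
| 0 | 5.0% | 5.0% |
| 0.1 | 7.8% | 10.9% |
| 0.2 | 16.5% | 29.3% |
| 0.3 | 31.2% | 56.4% |

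In the opposite direction, suppose the true effect is 0.572 and the talk offsets it by b. Power at 48 per arm is Φ((0.572 − b)/0.2041 − 1.960). It falls from 0.80 to 0.6375, 0.4451 or 0.2650 for b = 0.1, 0.2 or 0.3. That effect size comes from the anxiety calculation, and anxiety is the outcome the talk reaches least, so these power figures are the less relevant of the two sets.

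**The case against.** Several objections have force.

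- **No item rates the talk itself.** This is correct. A reader might infer that both arms score the surgeon's talk. They do not: the ratings are collected after it, and some items are broad enough to include it.
- **Anxiety is only weakly exposed.** This is also correct. A reader might infer that a change in the talk passes straight into the anxiety rating that sized the trial. Item 3 asks about the period of surgery, so the route is mainly recall.
- **The background evidence concerns something else.** The Purpose section says "perioperative communication and attentiveness have been identified as the two most important determinants of perceived surgeon performance". The survey has no item on surgeon performance, so the sentence shows only that the authors regard communication as influential.
- **The percentages are generic.** Any bias of that size in any two-arm trial gives the same error rates. Different surgeons may also react in opposite directions and partly cancel; b stands for what is left.
- **Surgeon reaction may be part of the pathway under test.** Families are assigned to communication pathways, and on a pragmatic reading the surgeon's response belongs to the effect. But the pages are described as additional to the same usual-practice talk, and the hypothesis concerns updates at chosen moments. The talk is therefore better read as common to both arms.
- **Some surgeons speak before the case is finished**, so the talk may precede the third page. The incision page would normally have gone by then.
- **A live relay by research staff would be costly.** It would need someone available throughout operations of two hours or more, and could delay the pages. This stands against a relay, and the fix below does not use one.

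**Conclusion.** The pathway is real and should be closed: paging by arm from within the team, no masking of the surgeon, an unscripted talk, and a survey after it. It bears mainly on items 2, 4, 5 and 7, and less on item 3. The size is unknown. The range of 0.1 to 0.3 SD is an assumption, and the table in the working also assumes a two-sided test.

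The documents do not support a stronger reading. They do not say that surgeons are told the arm, that any surgeon changes behaviour, or that the trial's false-positive rate is any of the figures shown. Whether the surgeon in fact learns the arm depends partly on who on the team sends the pages, which the protocol leaves open.

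**What to change.** In the Lay Language Summary and in Procedures:

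1. Have the surgical-team member send the same three pages at the same three events in every case, to a case-specific pager number supplied by the research team. In intervention cases the family holds that pager; in control cases the number reaches a pager not given to the family. The operating-room step is then identical in both arms, intervention families get the pages as planned, and no live relay is needed.
2. State that the operating surgeon is not told the arm before the final talk with the family.
3. Add the time of the talk to the research-team form, in both copies of the survey and for both arms. Together with the time out of the operating room, already on the form, this allows the timing to be compared by arm. Use it as a check and not as an adjustment covariate, because it arises after assignment.

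The cost is a few seconds per control case, some spare pagers, and one extra line on the form. Masking will be imperfect, since families know whether they were paged and may tell the surgeon. The change does nothing about families' own knowledge of their arm when they complete the survey. The recorded time can reveal a shift in timing but not in content.
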